# 8.6.6 Intervertebral Posterior Angle

For the intervertebral posterior angle, descriptive statistics will be calculated for time point to draw a time-course change plot. The percentage of the patients who showed a posterior intervertebral angulation angle of  $\geq$ 5° and associated 95% CIs will be calculated and presented.

Association between posterior intervertebral angulation and leg pain (VAS) or back pain (VAS) will be assessed.

# 8.6.7 Vertebral Body Translation

For the vertebral body translation, descriptive statistics will be calculated at each time point to make a time-course change plot. The percentage of the patients who showed a vertebral body translation of  $\geq$ 3 mm and associated 95% CIs will be calculated and presented.

Association between vertebral body translation and leg pain (VAS) or back pain (VAS) will be assessed.

# 8.6.8 Change in Bone Marrow Adjacent to Vertebral Endplates (Modic Classification)

Modic classifications will be displayed in a tabular form using frequencies by observation day. Shift tables will also be constructed to display Modic classifications. These tables will illustrate the change in a patient's classification between baseline and follow up visits.

For Modic classifications, proportions of patients with Modic's Type 0, Type 1, Type 2, and Type 3 will be calculated. In addition, proportions of patients (for each of Type 1, Type 2, and Type 3) whose Modic's types changed from "No" to "Yes" and associated 95% CI will also be calculated and presented.

A cross-tabulation of patients with any Modic's types changing from "No" to "Yes" and patients with AEs associated with leg pain and back pain will be displayed. In addition, changes from baseline of leg pain (VAS) and back pain (VAS) across time will be displayed separately for those 2 different Modic groups.

# 8.6.9 Disc Degeneration (Pfirrmann Classification)

Pfirrmann classifications will be tabulated to display the proportion of patients per observation day. Shift tables will also be constructed to display Pfirrmann classifications. These tables will illustrate the change in a patient's classification between baseline and follow-up visits.

For Pfirrmann classifications, proportions of patients with Pfirrmann's Grade 0, Grade I, Grade II, and Grade III will be calculated.

The percentage of patients whose Pfirrmann's grade increased with respect to the grade at baseline and associated 95% CIs will be calculated, analyzed and presented.

A cross-tabulation of patients whose Pfirrmann's grade increased with respect to the grade at baseline and patients with AEs associated with leg pain and back pain will be displayed. In addition, changes from baseline of leg pain (VAS) and back pain (VAS) across time will be displayed separately for those 2 different Pfirrmann groups.

#### 8.6.10 Occurrence of Post-Treatment Lumbar Surgery

As to occurrence of post-treatment lumbar surgery, the percentage of the patients having such surgery will be calculated and presented. In addition, the percentage of the patients with post-treatment lumbar surgery at the site of treatment injection and the percentage of the patients with post-treatment lumbar surgery at other sites will be calculated and reported.

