Criteria for Evaluation of Safety	
 
The following safety endpoints will be assessed:
 
Occurrence of adverse events (AEs)
 
Stability evaluation of vertebral bodies by X-ray 
 
Translation of vertebral body
 
Vertebral body angle formed by flexion
 
 
 
Changes from baseline in disc height (disc index) assessed by X-ray
 
Changes of disc degeneration and vertebral body endplates, and adjacent bone marrow as assessed by MRI 
 
Modic classification
 
Pfirrmann classification
 
Clinically significant changes in vital signs
 
Clinically significant changes in clinical laboratory tests
 
 
 
Serum anti-SI-6603 antibody
 
Occurrence of post-treatment lumbar surgery other than surgery for lumbar disc herniation at the same level of the investigational drug
 

Criteria for Evaluation of Efficacy	The following secondary efficacy endpoints will be assessed from baseline through Week 26:
of Lineacy	
 
Worst leg pain during the past 24 hours assessed by Visual Analog Scale (VAS).
 

	
 
Worst back pain during the past 24 hours assessed by VAS.
 
Functional disability measured by the Oswestry Disability Index (ODI).
 

	• Change of neurological status from baseline determined by neurological examinations (Femoral Nerve Stretching [FNS] test [for patients with lumbar disc herniation L1–L2, L2–L3, or L3–L4] or Straight Leg Raising [SLR] test [for patients with lumbar disc herniation L4–L5 or L5–S1], sensation, muscle strength, and deep tendon reflex).
	• Occurrence of post-treatment surgery for lumbar disc herniation at the same level of administration of the investigational drug up to Week 26 including patients who discontinued from the study.

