#### 1.2 Rationale

#### 1.2.1 Study Rationale

Lumbar disc herniation is treated primarily with conservative non-operative therapy. However, in patients who fail to respond to this therapy, surgery is one of the only remaining options. The target population of this study is patients with signs and symptoms of lumbar disc herniation who failed conservative therapy and who have not received surgery at the target level or who qualify for surgery but wish to avoid it. Patients who require immediate surgical intervention such as those with significant neurologic deficit will be excluded.

The results of the Japanese Phase II/III clinical study (Study Number: 6603/1021) suggest that SI-6603 intradiscal injection is safe and effective in improving the signs and symptoms of lumbar disc herniation. In addition, the Japanese Phase III clinical study (Study Number: 6603/1031) verified that SI-6603 intradiscal injection is safe and effective in improving the signs and symptoms of lumbar disc herniation. Therefore, conducting a further clinical study intended to assess safety and efficacy of intradiscal SI-6603 at a dose of 1.25 U was proposed.

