# Figure 1: Study Design

#### **3.2** Criteria for Evaluation of the Study

#### 3.2.1 Safety Endpoints

The following safety endpoints will be assessed:

- Occurrences of AEs
- Stability evaluation of vertebral bodies by X-ray at the times specified in the schedule of events
  - Translation of vertebral body
  - Vertebral body angle formed by flexion
- Changes from baseline in disc height (disc index) assessed by X-ray at the times specified in the schedule of events
- Changes of disc degeneration, vertebral body endplates, and adjacent bone marrow assessed by MRI at the times specified in the schedule of events
  - Modic classification
  - Pfirrmann classification
- Clinically significant change in vital signs at the times specified in the schedule of events
- Clinically significant change in clinical laboratory tests at the times specified in the schedule of events
- Serum anti-SI-6603 antibody at the times specified in the schedule of events
- Occurrence of post-treatment lumbar surgery other than surgery for lumbar disc herniation at the same level of the investigational drug administration

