#### 3.2.2 Secondary Efficacy Endpoints

The following secondary efficacy endpoints will be assessed at the times specified in the schedule of events and overall time-course, and changes from baseline will be analyzed:

- Worst leg pain during the past 24 hours assessed by VAS.
- Worst back pain during the past 24 hours assessed by VAS.
- Functional disability measured by the Oswestry Disability Index (ODI).
- Change of neurological status from baseline determined by neurological examinations:
  - Femoral Nerve Stretching (FNS) test for patients with lumbar disc herniation L1–L2, L2–L3, or L3–L4 or
  - Straight Leg Raising (SLR) test [for patients with lumbar disc herniation L4–L5 or L5–S1, and
  - Sensation, muscle strength, and deep tendon reflex.
- Occurrence of post-treatment surgery for lumbar disc herniation at the same level of administration of the investigational drug up to Week 26 including patients who discontinued from the study.

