#### 4.3.1 Patient Withdrawal Criteria

The Investigator will withdraw a patient from the clinical study if any of the following situations occur:

- 1. When the patient withdraws his or her consent
- 2. When the occurrence of an AE, such as noted below, leads the Investigator to judge it necessary for the patient to have surgical intervention or to withdraw the patient from the clinical study:
  - Significant neurologic deficit, e.g., progressive weakness or sudden loss of muscle strength in L1–L2, L2–L3, L3–L4, L4–L5 or L5–S1 innervated muscles, bowel or bladder dysfunction, or other signs and symptoms of cauda equine/conus medullaris involvement, or
  - Abnormal X-ray or MRI findings coupled with correlating clinical symptoms posing safety concerns
- 3. When a poor response to the investigational drug leads the Investigator to judge it necessary to perform a surgical intervention for back pain/leg pain or to withdraw the patient from the clinical study

- 4. If the Investigator judges it inappropriate to include a patient in the efficacy/safety assessment
- 5. If a patient becomes pregnant
- 6. Others:
  - No investigational drug could be administered.
  - The continuation of the study makes the risk to a patient's health unacceptable.
  - The Sponsor prematurely terminates the study.
  - The Investigator judges it necessary to withdraw a patient from the study.

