#### 8.1.2 Analysis Sets

The following populations will be assessed:

- Safety: All patients who were treated with an investigational drug.
- Intent-to-Treat (ITT): All patients who were treated with an investigational drug.

If considered necessary, further populations may be defined in the SAP.

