#### 8.5 Efficacy Analyses

Efficacy analyses will be performed for the ITT population.

The following efficacy endpoints will be analyzed using the appropriate parametric or nonparametric statistical method:

- Worst leg pain during the past 24 hours assessed by VAS from baseline through Week 26
- Worst back pain during the past 24 hours assessed by VAS from baseline through Week 26
- Functional disability measured by the ODI from baseline through Week 26
- Change of neurological status from baseline determined by neurological examinations FNS or SLR test, sensation, muscle strength, and deep tendon reflex) from baseline through Week 26
- Occurrence of post-treatment surgery for lumbar disc herniation at the same level of administration of the investigational drug up to Week 26

The descriptive statistics of the worst leg pain, back pain, ODI, and their change from baseline will be calculated and presented for each time point. A longitudinal plot will be used to display the mean change from baseline and the associated 95% confidence intervals (CIs) at each time point.

For analysis of change of neurological status from baseline, the number (%) of patients with negative FNS or SLR test results, negative neurological tests for hypoesthesia, muscle weakness, or diminished deep tendon reflex results will be presented for each time point. Furthermore, the percentage of patients with a negative neurological test will be calculated and presented for each time point. The time-course changes will also be presented graphically with bar chart by time points.

In the analysis of occurrence of post-treatment surgery for lumber disc herniation at the same level of administered disc, the number (%) of patients having such surgery will be calculated and presented.

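### Does Section 8.6.10 fail to report the surgical safety endpoint because it splits lumbar surgery by site and not by indication?

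*Combined protocol and SAP*

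**What the plan says.** Section 3.2.1 lists as a safety endpoint: "Occurrence of post-treatment lumbar surgery other than surgery for lumbar disc herniation at the same level of the investigational drug administration". The synopsis has the same exclusion: "Occurrence of post-treatment lumbar surgery other than surgery for lumbar disc herniation at the same level of the investigational drug". Whether an operation counts therefore depends on both the level and the reason for it.

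The excluded operations form a separate efficacy endpoint. Section 8.5 lists it as "Occurrence of post-treatment surgery for lumbar disc herniation at the same level of administration of the investigational drug up to Week 26", and Section 3.2.2 gives the window as "up to Week 26 including patients who discontinued from the study".

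Section 8.6.10, under Safety Analyses, gives three percentages: patients with post-treatment lumbar surgery, "the percentage of the patients with post-treatment lumbar surgery at the site of treatment injection", and patients with such surgery at other sites. It mentions no indication and does not refer back to Section 3.2.1.

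Three other places bear on the point:

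- The statistical part of the synopsis says that the primary objective is assessed through the listed safety endpoints. It promises an incidence with a 95% CI for adverse events and similar analyses for the other categorical safety endpoints.
- Section 8.1.2 defines the two analysis sets identically. The efficacy set is "Intent-to-Treat (ITT): All patients who were treated with an investigational drug", and the Safety set has the same wording.
- The opening of Section 8 describes its content as an outline and leaves detailed methods to a SAP finalised before database lock. That SAP is not part of the text reviewed.

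**The concern.** The endpoint is defined by level and indication, while its apparent analysis splits by level only. Read literally:

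- the overall percentage includes same-level herniation surgery, which the endpoint excludes;
- the injection-site percentage includes it too, and omits other levels;
- the other-sites percentage omits same-level surgery done for another reason.

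The excluded category need not be empty. The target population includes patients "who qualify for surgery but wish to avoid it" (Section 1.2.1), and one withdrawal criterion in Section 4.3.1 covers a poor response that leads the investigator to "judge it necessary to perform a surgical intervention for back pain/leg pain".

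If the literal reading were applied, operations that reflect lack of efficacy would also appear under safety, and a reader wanting the listed endpoint would have to derive it from two sections.

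**Working it through.** **1. The plan's own precision figures.** Section 8.8 gives Clopper-Pearson 95% limits for n = 1000. With x events, the lower limit is the 2.5% quantile of Beta(x, n − x + 1) and the upper limit is the 97.5% quantile of Beta(x + 1, n − x).

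- x = 3: 0.062% to 0.874% (stated: 0.06% to 0.87%).
- x = 15: 0.842% to 2.462% (stated: 0.84% to 2.46%).

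Both are reproduced. The same method is used below.

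**2. Definitions as cells.** Per 1000 treated patients, each in one cell:

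- H: herniation surgery at the injected level only
- S: surgery at the injected level for another reason only
- O: surgery at another level only
- D: herniation surgery at the injected level and surgery at another level

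Then:

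- 8.6.10 overall, literal = H + S + O + D
- 8.6.10 injection site, literal = H + S + D
- 8.6.10 other sites = O + D
- 8.5 count = H + D
- 3.2.1 endpoint = S + O + D
- overall minus 8.5 = S + O, which falls short of the endpoint by D

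In general, endpoint = overall − 8.5 count + patients who had both same-level herniation surgery and another lumbar surgery. The subtraction uses one denominator because the Safety and ITT sets coincide.

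**3. Numbers.** The documents give no surgery rates, so every count here is an assumption.

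| H, S, O, D | Overall, literal | Site, literal | Other sites | 8.5 | Endpoint (95% CI) | Overall − 8.5 |
|---|---|---|---|---|---|---|
| 40, 0, 5, 0 | 4.5% | 4.0% | 0.5% | 4.0% | 0.5% (0.16–1.16) | 0.5% |
| 40, 5, 5, 0 | 5.0% | 4.5% | 0.5% | 4.0% | 1.0% (0.48–1.83) | 1.0% |
| 40, 5, 5, 3 | 5.3% | 4.8% | 0.8% | 4.3% | 1.3% (0.69–2.21) | 1.0% |
| 0, 5, 5, 0 | 1.0% | 0.5% | 0.5% | 0.0% | 1.0% (0.48–1.83) | 1.0% |

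In the second row none of the three literal figures equals the endpoint, but subtraction gives it exactly. In the third row three overlap patients make the subtraction 1.3 − 1.0 = 0.3 percentage points too low. In the first row there is no same-level surgery for another reason, and the other-sites figure is already the endpoint.

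**4. Range.** Fix S = 5, O = 10, D = 0, so the endpoint is 15 of 1000, or 1.5%. With H = 10, 35 or 80 the literal overall count is 25, 50 or 95, that is 2.5% (1.62–3.67), 5.0% (3.73–6.54) or 9.5% (7.75–11.49). The contrast comes entirely from the value chosen for H, and H is what Section 8.5 reports. Subtraction gives 15 each time.

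**5. The other reading.** Suppose that lumbar surgery in Section 8.6.10 is shorthand for the 3.2.1 endpoint. In the second row of the table the three percentages become 1.0%, 0.5% and 0.5%: the endpoint, followed by its split by site. Nothing then has to be derived.

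**6. Direction.** The literal overall figure contains every endpoint patient, so it can only equal or exceed the endpoint. It cannot hide a safety event.

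**The case for a change.** The best argument for a change is that safety is the primary objective and the study has one arm, so the reported percentage is itself the result. The authors could write the distinction, since Section 8.5 names both level and indication, and Section 8.6.10 omits the second. Subtraction is exact only without overlap. Section 5.8.2 requires a patient who needs lumbar surgery to be discontinued, which may make second operations rare. Surgery is nevertheless recorded to Week 26 after discontinuation (Table 3, footnote e), so a second operation would be captured. Section 8.6.10 also states no confidence interval, although Sections 8.6.8 and 8.6.9 do. Pointing to a later SAP does not say which reading its author will take.

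What stands is that the wording is ambiguous and the two readings can give different figures. The rest is weaker. The synopsis already commits to the listed endpoint and, for categorical safety endpoints, to an incidence with a 95% CI, so Section 8.6.10 need not be read alone. Same-level herniation surgery has its own analysis under efficacy, which favours reading the safety section as covering the remainder. Sections 1.2.1 and 4.3.1 show that surgery after a poor response is foreseen. They do not show that surgery at the injected level for reasons other than herniation is expected, and that is the cell on which a mismatch with the other-sites percentage depends.

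**Conclusion.** The ambiguity is real, but no change to the plan follows. This is a gap that an analyst fills sensibly from Sections 3.2.1 and 8.5 and the synopsis. Identifying the Section 8.5 operations already requires level and indication, so the analyst has the basis for separating them from the rest. Saying in a table title which operations are counted is ordinary content for the SAP that Section 8 promises.

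On the least favourable reading, the output would be three accurate percentages by site, the first of which can only overstate the endpoint, alongside a separate count of the operations that make the difference. Under the assumed counts the literal figure exceeds the endpoint by 4.0 percentage points (5.0% against 1.0%), all of it reported in Section 8.5. The part not recovered by subtraction is the overlap, 0.3 points if 3 patients per 1000 had both kinds of surgery. These sizes rest on assumed counts. The conclusion rests on the definitions and on the shared denominator. No test, sample size or decision rule uses the percentage, and the termination conditions tied to adverse events in Section 9.10 do not refer to it.

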#### 8.7 Interim Analyses

No interim analysis is planned.

# 8.8 Determination of Sample Size

The total number of 1000 patients will be enrolled. In order to further characterize the frequency and outcome of the rather infrequent treatment-related AE, the current study will have approximately 1000 patients treated with SI-6603. This sample size will allow for estimating a cumulative incidence rate of 0.3% (n=3 patients with events) with a 95% CI of (0.06%, 0.87%), or an incidence rate of 1.5% (n=15 patients with events) with a 95% CI of (0.84%, 2.46%). This calculation assumes that distribution of treatment-related AE is binomially distributed. The 95% CI is calculated using the Clopper-Pearson method in SAS 9.2.

# 9 ETHICAL, LEGAL, AND ADMINISTRATIVE ASPECTS

#### 9.1 Data Quality Assurance

The Sponsor (or Sponsor's designated agent) will conduct a site visit to verify the qualifications of each Investigator, inspect the site facilities, and inform the Investigator of responsibilities and the procedures for ensuring adequate and correct documentation.

The Investigator is required to prepare and maintain adequate and accurate case histories designed to record all observations and other data pertinent to the study for each study participant. All information recorded in the eCRF for this study must be consistent with the patients' source documentation (i.e., medical records).

#### 9.1.1 Database Management and Quality Control

All data generated by the site personnel will be captured electronically at each study site using eCRFs. Data from external sources (such as laboratory data) will be imported into the database. Once the eCRF clinical data have been submitted to the central server at the independent data center, corrections to the data fields will be captured in an audit trail. The reason for change, the name of the person who performed the change, together with the time and date will be logged to provide an audit trail.

If additional corrections are needed, the responsible monitor or data manager will raise a query in the eCRF page. The appropriate staff at the study site will answer queries sent to the Investigator. The name of the staff member responding to the query, and time and date stamp, will be captured to provide an audit trail. Once all source data verification is complete and all queries are closed, the monitor will freeze the eCRF page.

The specific procedures to be used for data entry and query resolution using the eCRF will be provided to study sites in a training manual. In addition, site personnel will receive training in the eCRF.

#### 9.2 Case Report Forms and Source Documentation

All data obtained during this study should be entered in the eCRFs promptly. All source documents from which eCRF entries are derived should be placed in the patient's medical records. Measurements for which source documents are usually available include laboratory assessments, MRIs, and X rays.

The original eCRF entries for each patient may be checked against source documents at the study site by the PAREXEL site monitor.

After review by the site monitor, completed eCRF entries will be uploaded and forwarded to PAREXEL. Instances of missing or uninterpretable data will be discussed with the Investigator for resolution.

The specific procedures to be used for data entry and query resolution using the eCRF will be provided to study sites in a training manual. In addition, site personnel will receive training in the eCRF.

# 9.2.1 Data collection

The Investigators (and appropriately authorized staff) will be given access to an eCRF system which is 21 CFR Part 11 compliant. This system is specifically designed for the collection of the clinical data in electronic format. Access and right to the eCRF system will be carefully controlled and configured according to each individual's role throughout the study. In general, only the Investigator and authorized staff will be able to enter data and make corrections in the eCRFs.

The eCRF should be completed for each patient included in the study and should reflect the latest observations on the patients participating in the study. Therefore, the eCRFs are to be completed as soon as possible during or immediately after the patient's visit or assessment. The Investigator must verify that all data entries in the eCRF are accurate and correct. If some assessments cannot be done, or if certain information is unavailable, not applicable or unknown, the Investigator should indicate this in the eCRF.

Computerized data-check programs and manual checks will identify any clinical data discrepancies for resolution. Corresponding queries will be loaded into the system and the site will be informed about new issues to be resolved on-line. All discrepancies will be solved on-line directly by the Investigator or by authorized staff. Off-line edit checks will be done to examine relationships over time and across panels to facilitate quality data.

After completion, the Investigator will be required to electronically sign off the clinical data.

Data about all study drug dispensed to the patient and any dosage changes will be tracked on the eCRF.

